11.3. Analysis Populations

The Full Analysis Set (FAS), used for all of the efficacy analyses, is defined as all randomized patients. The FAS is also known as the intention-to-treat (ITT) set of patients. Patients in the FAS will be included in their randomized treatment group, regardless of the treatment they actually received.

The Safety Population (SP), used for all of the safety summaries, is defined as all randomized patients who received at least 1 dose of study medication. Patients in the SP will be included in the treatment group that they actually received, regardless of their randomized treatment.

11.4. Disposition, Demographics and Baseline Characteristics

Disposition, including reason for withdrawal from the study, will be summarized by treatment group. Demographic information and patient characteristics including, but not limited to, gender, race, age, and baseline vital signs will also be summarized by treatment group.

11.5. Primary Endpoint Analysis

The primary efficacy endpoint is the percent change from baseline to Week 12 in LDL-C. Baseline is defined as the mean of the values from Week -1 (Visit S3) and predose Day 1/Week 0 (Visit T1).

The primary efficacy endpoint will be analyzed using analysis of covariance (ANCOVA), with treatment group and patient type (primary prevention; secondary prevention) as factors and

baseline LDL-C as a covariate. The ANCOVA will be performed using the FAS, with patients included in their randomized treatment group regardless of the treatment they actually received. The details of the ANCOVA model and options to account for unequal variances and group size will be described in the SAP.

Missing data for the primary endpoint will be imputed using a multiple imputation method that accounts for treatment adherence. A pattern mixture model (PMM) will be used to specify different imputation strategies depending on whether the patient is still on study treatment. Patients with missing LDL-C data at Week 12 who are no longer taking study treatment can be assumed no longer to be benefitting from study medication, and their missing value(s) can be assumed to be similar to those from placebo patients. In this instance, it is reasonable to impute LDL-C values in a model including placebo patients' data only. Patients with missing LDL-C data at Week 12 who are still taking study treatment can be assumed to continue to benefit from study medication, and their missing value(s) can be assumed to be similar to those who remain on study treatment and have data. In this instance, it is reasonable to impute LDL-C values based on the observed values in their randomized treatment group at Week 12. Details for the PMM will be described in the SAP.

To account for uncertainty, missing values will be imputed using multiple imputation. Imputed datasets will be analyzed using an ANCOVA model with the treatment and patient type (primary prevention; secondary prevention) as factors and baseline LDL-C as a covariate. Approximately 200 imputed datasets will be created, with results from the analysis of each imputed dataset combined using Rubin's method. For each type of ANCOVA (observed case; imputation via PMM), the least squares mean (LSM) and standard error (SE) will be provided for both treatment groups, along with the placebo-corrected LSM, its 95% confidence interval (CI) and associated p-value.

11.6. Secondary and Tertiary Endpoint Analysis

Secondary efficacy endpoints are also of interest for this study, in terms of controlling the overall Type I error rate, a gatekeeping or stepdown approach will be used to test the primary efficacy endpoint and then specific secondary efficacy endpoints sequentially in order to preserve the study-wise Type I error rate. The sequence for the stepdown procedure in this study is as follows:

1. Test the primary efficacy endpoint: percent change from baseline to Week 12 in LDL-C
2. Test the percent change from baseline to Week 24 in LDL-C
3. Test the percent change from baseline to Week 12 in non-HDL-C
4. Test the percent change from baseline to Week 12 in TC
5. Test the percent change from baseline to Week 12 in apoB
6. Test the percent change from baseline to Week 12 in hs-CRP

In this hierarchical testing structure, each hypothesis is tested at a significance level of 0.05, two-sided. Statistical significance at each step is required in order to test the next hypothesis. If the primary endpoint meets the criteria for statistical significance, then the percent change from baseline to Week 24 in LDL-C will be tested; and so forth.

For the remaining secondary efficacy endpoints and the tertiary efficacy endpoints, a significance level of 0.05 will be used; given the large number of remaining endpoints, the p-values for those endpoints will be considered descriptive.

In general, change or percent change in lipid parameters at a given time point will be analyzed using similar ANCOVA model for the primary endpoint with treatment group and patient type (primary prevention; secondary prevention) as factors and the relevant baseline as a covariate.

Baseline for [REDACTED] non-HDL-C, [REDACTED] and TC is defined as the mean of the values from Week -1 (Visit S3) and predose Day 1/Week 0 (Visit T1). Baseline for apoB and hs-CRP is defined as the predose Day 1/Week 0 (Visit T1) value.

Each ANCOVA will be performed using the FAS, with patients included in their randomized treatment group regardless of the treatment they actually received. Same imputation method described for the primary endpoint will be used for those secondary endpoints included in the step-down procedure, while only observed data analysis will be used for other secondary and tertiary endpoints. For each lipid parameter and analysis time point, the LSM and SE will be provided for both treatment groups, along with the placebo-corrected LSM, its 95% CI and associated p-value.

The ANCOVA assumption of normality will be assessed. If severe non-normality of the data is found at any time point for any parameter, either the data will be transformed so that it is normally distributed or a nonparametric test will be considered instead of the planned ANCOVA.

Finally, the number and percent of patients in each treatment group requiring additional (post-randomization) TG-lowering therapy will be summarized. The medications will be summarized by treatment group.

11.7. Safety Analysis

The summarization of AEs will include TEAEs, defined as any unfavorable and unintended sign, symptom, or disease temporally associated with the use of the investigational product, whether or not related to the product. TEAEs and SAEs will be summarized by SOC, severity, and relationship to study drug for each treatment group. These AE summaries will include cumulative incidence (percent of patients experiencing the AE) and patient-year adjusted incidence rates. If appropriate, absolute and relative risk differences will be calculated using both cumulative incidence and incidence rates. Deaths, withdrawal from study treatment due to AEs, and withdrawal from the study due to AEs will each be summarized by treatment group.

Clinical safety laboratories, including hematology, blood chemistry, coagulation, HbA_{1C}, glucose, and urinalysis; PE findings; vital signs; ECG readings; and weight will be summarized by the value and by change from baseline in the value (where appropriate) at each post baseline time point.

Hepatic Safety

For liver-associated enzymes and TB, the number and percent of patients with abnormal values for ALT, AST, and TB will be summarized. Hy's law criteria ($\geq 3 \times$ ULN for either ALT or AST, with accompanying TB $> 2 \times$ ULN (conjugated [direct] if Gilbert's Disease) in the absence

of other known causes) will also be applied to the data; any potential Hy's law cases will be listed separately.

Musculoskeletal Safety

AEs of muscle-related symptoms will be summarized by treatment group. In addition, the number and percent of patients with abnormal CK values will be summarized.

Diabetes/Glycemia

Cases of new onset of diabetes will be recorded as AEs and will be summarized using the appropriate SOC. These events will be summarized by severity and relationship to study drug for each treatment group.

Renal Safety

Baseline eGFR and values of CK will be summarized by treatment group and by baseline eGFR categories. Shift tables of eGFR category from baseline over the study, will be provided by treatment group. Finally, muscle-related AEs will be summarized by treatment group and by baseline eGFR category.

Neurocognitive Events

Neurocognitive events will be identified and evaluated by routine safety monitoring of PE findings and AEs. Summarization of neurocognitive events will occur using prespecified MedDRA terms and will be performed by treatment group.

Clinical endpoints

Clinical endpoints will be monitored and adjudicated by an independent blinded expert CEC for this study and other ongoing studies the bempedoic acid program. Adjudicated clinical endpoints will be summarized by event type and treatment group. Additional details regarding clinical endpoints and clinical endpoint definitions will be included in CEC charter.

11.8. Pharmacokinetics

Three plasma PK samples for analysis will be collected. Plasma concentrations of bempedoic acid and optionally, one or more of its metabolites, will be determined in patients who are receiving bempedoic acid. All patients, site personnel, and study personnel will remain blinded to treatment assignment throughout the duration of the study. Personnel performing the bioanalytical analysis of bempedoic acid concentrations will be unblinded in order to assay the appropriate samples during the study. Plasma concentrations of bempedoic acid and any measured metabolite will be included in the listings, but population PK analysis will be reported separately will be descriptive by time point.

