Clinical endpoints using standardized definitions will be adjudicated by an independent blinded expert CEC for all ongoing Phase 3 studies in the bempedoic acid program. Investigator-reported clinical endpoints and adjudicated clinical endpoints will be summarized by event type and treatment group. Additional details regarding the clinical endpoints and their definitions will be included in CEC Charter.

Pharmacokinetics

Three pharmacokinetic (PK) samples will be collected. Plasma concentrations of bempedoic acid and its metabolite ESP15228 will be determined in patients who are receiving bempedoic acid, who have compliance $\geq 80\%$, and who have taken a dose of bempedoic acid within 2 days of the sample collection. All patients, site personnel, and study personnel will remain blinded to treatment assignment throughout the duration of the study. Personnel performing the bioanalytical analysis of bempedoic acid concentrations will be unblinded in order to assay the appropriate samples during the study. Plasma concentrations of bempedoic acid and ESP15228 will be summarized using descriptive statistics by time point.

TABLE OF CONTENTS

1.	TITLE PAGE.....	1
2.	SYNOPSIS	2
3.	ABBREVIATIONS AND DEFINITIONS.....	20
4.	INTRODUCTION.....	25
4.1.	Overview of the Disease Under Study.....	25
4.2.	Overview of Bempedoic Acid	26
4.2.1.	Mechanism of Action	26
4.2.2.	Pharmacokinetics and Pharmacology	26
4.2.3.	Dose Selection	27
4.3.	Nonclinical Experience.....	27
4.4.	Clinical Experience.....	27
5.	STUDY OBJECTIVES AND ENDPOINTS.....	29
5.1.	Study Objectives	29
5.1.1.	Primary Objective	29
5.1.2.	Secondary Objectives	29
5.1.3.	Tertiary Objective.....	29
5.2.	Study Endpoints.....	29
5.2.1.	Primary Endpoint.....	29
5.2.2.	Secondary Endpoints	29
5.2.3.	Tertiary Endpoints	29
5.2.4.	Safety Endpoints.....	30
6.	INVESTIGATIONAL PLAN.....	30
6.1.	Overall Study Design.....	30
6.2.	Study Population and Selection.....	30
6.2.1.	Inclusion Criteria	31
6.2.2.	Exclusion Criteria	33
6.3.	Patient Identification, Randomization, and Blinding	36

7.	INVESTIGATIONAL MEDICINAL PRODUCT	38
7.1.	Investigational Medicinal Product Supply and Control.....	38
7.2.	Administration of Investigational Medicinal Product	38
7.3.	Concomitant Medications	39
7.3.1.	Lipid-Regulating Medications and Supplements.....	39
7.3.2.	Prohibited Medications	40
7.3.3.	Allowable Medications	41
7.4.	Patient Lifestyle and Dietary Guidelines.....	41
7.5.	Treatment Compliance.....	41

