11. STATISTICS

11.1. General Considerations

The statistical analyses described in this section will be performed as further outlined in a separate Statistical Analysis Plan (SAP). The SAP will supersede the protocol in the event of any differences between the 2 documents in relation to data analysis, and the protocol will be amended if appropriate. The SAP will be included as an appendix in the clinical study report for this protocol.

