### 5.4. PK ANALYSIS SET [PKS]

The PK Analysis Set will include all subjects in the safety analysis set who have at least one non-missing PK assessment. These subjects will be evaluated for PK concentration summaries unless major protocol deviations are identified during the protocol deviation review or if key dosing or sampling information is missing.

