### 17.1. DERIVATIONS

Compliance with placebo-run in (as an overall group) and double-blind study medication by treatment group—based on the drug accountability data—will be calculated as the number of tablets taken (total dispensed – total returned) divided by the number of days on treatment within each of the 2 periods.

During the run-in period, the compliance will be summarized as a single overall group and during the double-blind period, compliance will be summarized by treatment group (bempedoic acid and placebo).

Compliance will not be computed by visit.

A 35-day supply of single-blind placebo drug will be dispensed one time at Week -4 (Visit S2) for the 4-week placebo run-in period of the study. Double-blind IMP will be dispensed in 100 day supply increments to patients by appropriate clinical site personnel. Patients will receive one 100-day supply bottle at Week 0 (Visit T1).

The treatment is taken once daily and it is assumed that the patient takes medication on the visit day at which their medication is initially dispensed to the date of last dose as captured on the End of Treatment eCRF page. For example, if the initial dispense date is Day 1 and the last dose is Day 84, then the patient should have taken the first tablet at Day 1, once a day on Days 2 to 83 and 1 tablet on Day 84; hence, the total number of prescribed tablets would be 84.

For subjects who did not return any bottle during the double-blind period, their compliance will be set to missing.

Treatment exposure will be calculated in weeks as (date of last dose of study medication – first date of first dose of study medication +1)/7. Descriptive statistics will be presented for exposure as well as categorization into time periods (e.g., <12weeks, >=12 weeks to <24 weeks, >=24 weeks, etc.).

[REDACTED]

Version Number: 1.7  
 Version Date: 21Mar2018

[REDACTED]

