## 19.8. PHARMACOKINETICS

Descriptive statistics for concentrations of bempedoic acid and its metabolite ESP15228 will be presented for each visit weeks 4, 8, and 12 if the PK sample time is within 18-30 hours of the last dose of IMP. All concentration data will also be presented in a listing. All concentrations below the limit of quantification or missing data will be labelled as such in the concentration data listings. Concentrations below the lower limit of quantification will be treated as zero in summary statistics.

[REDACTED]

Version Number: 1.7  
 Version Date: 21Mar2018

[REDACTED]

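### The protocol synopsis and Section 11.8 disagree on which PK samples and analytes are assayed, and the SAP's precedence does not settle it

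*Protocol*

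**What the plan says.** Two current protocol passages say whose concentrations are measured.

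- **Protocol 11.8:** "Plasma concentrations of bempedoic acid and optionally, one or more of its metabolites, will be determined in patients who are receiving bempedoic acid". There is no compliance or timing condition, and metabolites are optional. The values go to listings and to a separately reported population PK analysis.
- **Protocol synopsis, Pharmacokinetics:** bempedoic acid and ESP15228 are both named. The patients are those receiving bempedoic acid whose compliance is at least 80% and "who have taken a dose of bempedoic acid within 2 days of the sample collection". The period for the 80% is not given.

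Both passages have the laboratory assaying samples while the study is running.

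The SAP says which values are summarized. Section 19.8 plans descriptive statistics for both analytes "if the PK sample time is within 18-30 hours of the last dose of IMP", with no compliance condition, and a listing of all concentrations. Section 5.4 admits safety-set subjects with at least one non-missing PK assessment to the summaries "unless major protocol deviations are identified during the protocol deviation review or if key dosing or sampling information is missing".

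On precedence, Protocol 11.1 states: "The SAP will supersede the protocol in the event of any differences between the 2 documents in relation to data analysis".

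On compliance, SAP 17.1 uses tablets taken "divided by the number of days on treatment within each of the 2 periods" and adds: "Compliance will not be computed by visit". The value is missing for a patient who returns no bottle in the double-blind period. Protocol 7.5 has sites count returned tablets at each treatment-period visit.

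**The concern.** Assay comes before analysis: a sample that is never assayed cannot be recovered by a rule about which values to summarize. The precedence clause covers differences between SAP and protocol on data analysis. It does not reach a conflict between two protocol sections about laboratory work, so the laboratory could follow either one.

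Each choice loses something. Under the synopsis, samples are withheld according to adherence. A patient whose samples are all withheld would, on a literal reading of SAP 5.4, have no PK assessment and so fall outside the PK Analysis Set. Under 11.8, omitting the optional metabolite would leave the ESP15228 statistics in SAP 19.8 with no data.

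**Working it through.** **Step 1. The rules side by side.**

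| | Protocol 11.8 | Protocol synopsis | SAP 19.8 with 5.4 |
|---|---|---|---|
| Stage | assay | assay | summary |
| Compliance | none | at least 80%, period undefined | none |
| Time since dose | none | within 2 days | 18-30 h |
| ESP15228 | optional | yes | yes |
| Other exclusions | none | none | major deviations; missing dosing or sampling data |

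The last column is fixed by the precedence clause. The first two conflict and nothing resolves them.

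**Step 2. Which synopsis condition can affect the SAP summary?** A sample taken 18-30 h after dose was also taken within 48 h. The 2-day condition therefore removes nothing that the SAP window would keep. Only the compliance condition can change the summary.

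**Step 3. Does the compliance period matter?** Over 24 weeks of once-daily dosing there are 24 × 7 = 168 tablets.

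- None of 28 tablets before Week 4 and all later ones: 140/168 = 83.3%. The patient passes on a full-period figure despite no drug before the Week 4 sample.
- 84 of 84 to Week 12, then 50 of 84: 134/168 = 79.8%. The patient fails on a full-period figure despite full adherence at the Week 4 and Week 12 samples.

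A figure up to each sample would classify the relevant visits the other way. The synopsis does not say which is meant.

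**Step 4. Size of the selection.** The documents give no adherence distribution, so this rests on assumptions: one compartment, half-life 15 or 27 h (the ends of the range in Protocol 4.2.2), independent daily dosing, 5-30% poor adherers taking 50-70% of doses, all others taking 97%, and sampling-time SD 2 h. Results are for Week 4, with compliance taken over the full period.

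| Rule | Mean trough as share of full-adherence trough | Share of samples kept |
|---|---|---|
| SAP window alone | 0.94-0.99 | 83-95% |
| SAP window after the synopsis rule limits assay | 0.98-0.99 | 68-92% |

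Within a scenario, the smallest shift is 0.994 - 0.991 = 0.003 (half-life 15 h, 5% poor adherers at 70% of doses). The largest is 0.985 - 0.939 = 0.046 (27 h, 30% at 50%). The added upward shift is therefore about 0.3 to 4.6 percentage points.

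**Step 5. Samples at stake.** With 200 patients planned on bempedoic acid and three samples each, at most 600 samples are drawn in that arm. If 5-15% of patients fell below 80% (an assumption), that is 10-30 patients. If each lost all three samples, 30-90 would go unassayed.

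**Step 6. Visit list.** Protocol 10.1.6.2 and the schedule of events place PK sampling at T2, T4 and T5, that is Weeks 4, 12 and 24. SAP 19.8 summarizes Weeks 4, 8 and 12. Week 8 is a telephone visit (Protocol 8.3.6). As written, Week 8 has no data and Week 24 has no summary.

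**The case against.** The strongest reply is that the planned summary is already settled. The SAP overrides the protocol on analysis, its window is explicit, and it has no compliance condition. That stands: the three sets of conditions are not rivals for the summary. It leaves open which samples have a value to summarize.

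Four stronger readings are tempting, and the documents do not support them.

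- **Samples up to 48 hours old pull the summary down.** They cannot, because the SAP window excludes them (Step 2).
- **The compliance rule cannot be applied, because the SAP does not compute compliance by visit.** The SAP derivation is for reporting, and the synopsis does not adopt it. Tablets are counted at T2, T4 and T5, so compliance up to each sample could be worked out. The rule is undefined rather than unusable.
- **The trough summary is biased.** The PK output is descriptive and names no target. If the target is the trough under dosing as directed, restricting to adherent patients moves the mean closer to it.
- **ESP15228 will not be measured.** Section 11.8 permits its measurement, and the synopsis and SAP name it. The risk comes from loose wording and is not a plan to omit the metabolite.

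**Conclusion.** The conflict between the synopsis and Section 11.8 on assay eligibility and the metabolite is real and unresolved. It is minor. Only descriptive and population PK are affected; the primary endpoint, the testing hierarchy and power are not.

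If the synopsis controls the assay and the target is exposure in all treated patients, the Week 4 mean trough is shifted upward by an amount in the range shown in Step 4. That range depends wholly on the assumed adherence. The simulation also holds each patient's adherence constant over time, so it does not capture adherence that changes after a sample is drawn. If Section 11.8 controls, there is no such selection, but the ESP15228 summary is at risk. The visit mismatch in SAP 19.8 is a separate, definite error in the same section.

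**What to change.** 1. In the synopsis and Section 11.8, state that bempedoic acid and ESP15228 are assayed in every T2, T4 and T5 sample from patients who received bempedoic acid. Go by treatment received, because the PK Analysis Set sits within the safety set. Delete the compliance and 2-day conditions.
2. Keep the 18-30 h window in SAP 19.8, together with the exclusions in SAP 5.4, as the summary rule. List all other values with hours since last dose.
3. In SAP 19.8, change the summary visits to Weeks 4, 12 and 24.

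The cost is a wording change in both documents and the assay of a small number of samples that are drawn anyway.

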11.9. Interim Analysis and Data Monitoring Committee

There are no planned interim analyses for this study. An independent DMC will review accumulating unblinded safety data from this study and other ongoing studies of bempedoic acid. Additional details regarding the DMC will be included in the DMC Charter.

